Additional clinical self-report outcomes (three PROMIS scales, BEAQ, CFS, and SMQ) were analyzed similarly to the primary endpoint using Bayesian mixed effects growth models with random intercepts, slopes, and their covariance. First, the optimal functional form of the temporal trend (i.e., linear or piecewise trajectory) was determined for each outcome variable by comparing nested unconditional models as previously described. Then, outcome variables with the same form of trajectory were simultaneously predicted in a multivariate mixed effects model, with level-1 residuals allowed to covary across outcomes, and separate (i.e., uncorrelated) blocks for level-2 random effects². For each outcome variable we assessed the existence of effects as well as the clinical significance of the between-treatment difference in change scores using the ROPE-full method, as defined by \pm 0.1* σ outcome baseline.

Secondary Endpoints – Physical Activity Measures

SPPB gait speed was analyzed in a two-way (treatment-by-time) mixed effects linear regression model with random intercepts, estimated via restricted maximum likelihood. The ANOVA-like specification was selected instead of the growth model as there were only two timepoints per participant.

In contrast, the large number of repeated observations for weekly average daily steps allowed for modeling potentially complex nonlinear trends. Step counts were analyzed using a multiple-group mixed effects model with a latent basis growth specification, estimated via maximum likelihood with the *nlme* package(Pinheiro et al., 2023). Initially, random effects for intercepts and total growth were included, but the model could not converge; thus, only random intercepts were retained. In the latent basis growth model, the optimal shape of the temporal trajectory is estimated directly from the data, similar to factor loadings in confirmatory factor analysis(Ram & Grimm, 2007). Two basis vectors, A_0 and A_1 , each with seven elements (corresponding to the number of measurement occasions per person), described the pattern of change over time separately within SG and TD groups. A_0 was a fixed vector of 1s, while A_1 contained two fixed elements for model identification – the first

² Across outcomes, we identified a single outlier value on the CFS that was non-credible (based on the subsequent and succeeding scores for that participant) and replaced that data point using multiple imputation.

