coefficient set to 0 and the last set to 1. The remaining five elements of A_1 were freely estimated, with each basis coefficient representing the proportion of total change occurring between the first and last measurement occasions. PerRam and Grimm (2009), the multiple-group growth model can be expressed as follows:

Avg Daily Steps[Visit]_n =
$$g_{0nc} * A_{0c}[Visit] + g_{1c} * A_{1c}[Visit] + e[Visit]_{nc}$$

The subscript c denotes the respective treatment group (SG or TD) for individual n, g_0 represents the expected starting value of weekly average daily steps, and g_1 represents the expected change in average daily steps from pre-treatment to 1-month follow-up .

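### The step model's basis coefficients are visit changes divided by net change: unidentified at zero net change and unstable near it, so they are unreliable as proportions of total change

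*SAP*

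**What the plan says.** The step analysis is in the SAP under Secondary Endpoints – Physical Activity Measures. The SAP chooses a latent basis model, in which "the optimal shape of the temporal trajectory is estimated directly from the data". On the random effects it reports: "Initially, random effects for intercepts and total growth were included, but the model could not converge; thus, only random intercepts were retained".

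There are two basis vectors, which "described the pattern of change over time separately within SG and TD groups", one element per occasion and seven in all. A_0 is a vector of ones. A_1 has its first "coefficient set to 0 and the last set to 1", and "The remaining five elements of A_1 were freely estimated". The SAP then interprets the vector, "with each basis coefficient representing the proportion of total change occurring between the first and last measurement occasions".

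In the model equation g_0 carries a person and an arm subscript, while g_1 carries only the arm subscript. The SAP defines g_1 as the expected change from pre-treatment to 1-month follow-up. It sets no condition on the size of g_1, names no interval method for A_1, and gives no alternative if g_1 is small.

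**The concern.** A latent basis model normally learns its shape from two sources: the mean trajectory, and the way people's individual growth covaries across occasions. Once the random growth term is removed, the second source is gone. A_1 then enters the model only through the product g_1 × A_1 in the arm mean. If g_1 is zero that product is zero whatever A_1 is, and if g_1 is small A_1 is a ratio with a poorly determined denominator.

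This matters because the model was chosen to describe complex nonlinear trends, and A_1 is the part that carries the shape. One plausible trend in a five-session behavioural treatment is a rise in steps during therapy that fades by the 1-month visit. That is the case in which net change is small and the ratio behaves worst. A reader shown A_1 as proportions could take noise for a shape, or see a real temporary rise displayed with a negative sign.

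**Working it through.** **Inputs from the documents.** Seven occasions; A_1 fixed at 0 and 1 at the ends with five free elements per arm; random intercepts only; g_1 without a person subscript (all SAP, Physical Activity Measures). Eight patients per arm (Protocol, Phase 2). This is an upper limit for step data, because the Protocol excuses users of assisted mobility devices from the pedometer.

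**Assumed, because the documents do not give them.** Within-person SD of weekly average steps, s = 800 to 1,600 (1,500 in one check); independent weekly errors; complete data. The between-person SD cancels in changes from the first visit. The plan states no precision or power for the step model, so there is no figure of its own to reproduce.

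**Step 1: what the coefficients are.** The arm mean at visit k is μ_k = g_0 + g_1 × A_1[k]. Setting A_1[1] = 0 and A_1[7] = 1 gives g_0 = μ_1 and g_1 = μ_7 − μ_1, so

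A_1[k] = (μ_k − μ_1) / (μ_7 − μ_1).

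Parameters per arm: 1 (g_0) + 1 (g_1) + 5 (free A_1) = 7, for 7 means. The mean model is saturated. A generalised least squares fit to one simulated arm gave A_1 = (−0.3883, 0.3975, 1.1926, 2.1843, 0.0691), identical to the ratios of sample mean changes. With missing weeks the same relation holds for the model-estimated means.

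**Step 2: identification.** Rank of the derivative of the means and covariances with respect to the parameters:

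| Random effects | g_1 | Rank |
|---|---|---|
| Intercept only | 0 | 4 of 9 |
| Intercept only | not 0 | 9 of 9 |
| Intercept and growth | 0 | 11 of 11 |

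The five lost dimensions in the first row are the five free A_1 elements. The last row shows that the discarded growth term would have identified them even at zero mean change.

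**Step 3: precision of the denominator.** SE(g_1) = s × √(2/8) = s/2. A Fieller 95% interval for any A_1[k] is bounded only if the estimate of g_1 exceeds t × SE in absolute value, with t = 2.018 on (8 − 1) × (7 − 1) = 42 degrees of freedom:

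- s = 800: SE 400, threshold about 807 steps
- s = 1,200: SE 600, threshold about 1,211 steps
- s = 1,600: SE 800, threshold about 1,614 steps

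At s = 1,500 with a mid-course change of 1,000 steps, the simulated share of unbounded intervals was 90% when true g_1 was 500, 74% at 1,000, 26% at 2,000 and 2% at 3,000.

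**Step 4: spread of the ratio.** Draws of (0.6g + e_k − e_1)/(g + e_7 − e_1), with each e distributed N(0, s²/8), so the true coefficient is 0.6 whenever g is not zero:

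| True net change g | Estimate outside 0 to 1, s = 800 | s = 1,600 |
|---|---|---|
| 0 (no true coefficient exists) | 67% | 67% |
| 500 | 49% | 62% |
| 1,000 | 22% | 49% |
| 2,000 | 2% | 22% |

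At g = 500 the central 95% of estimates runs from about −4.5 to 5.8 (s = 800) and −8.6 to 9.6 (s = 1,600).

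**Step 5: a temporary rise.** Mid-treatment change 1,000, net change 200, so the true coefficient is 1,000/200 = 5. The Wald interval uses the delta-method SE(A) = √(v + A²v − 2Ac)/|g_1|, with v = 2s²/8 and c = s²/8.

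| | s = 800 | s = 1,200 |
|---|---|---|
| Coefficient estimate negative | 30% | 34% |
| 95% Wald interval covers 5 | 68% | 59% |
| Wald interval for A_1 lies above 0 | 11% | 6% |
| Interval for the direct change (mean_k − mean_1) lies above 0 | 71% | 38% |

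The last two rows use the same data and the same likelihood.

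**The case against.** The strongest reply is that nothing in the fit itself is wrong. The fitted visit means and g_1 are exactly those of an arm-by-visit model, with the same precision. In the temporary-rise example most negative coefficients arise because the estimate of g_1 is negative, and the product g_1 × A_1 still shows the rise: the fitted mid-treatment change is below zero in only 0.6% (s = 800) and about 5% (s = 1,200) of trials. A plot of fitted means would not mislead. All of this stands, and it confines the point to reading A_1 by itself.

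Three further replies also stand. A value outside 0 to 1 is not in itself an error, since a trajectory that overshoots and falls back has true coefficients above 1; but such a value cannot be read as a proportion of total change either. The size depends on a step SD and an observed g_1 that the documents do not give. And the SAP describes this as analysis already completed, on a secondary endpoint of a pilot trial.

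A reader might infer that the coefficients cannot be estimated at all whenever net change is small. That goes too far: for any non-zero g_1 they are identified and computable, only poorly determined. A reader might also infer that the arms are compared on A_1, or that A_1 is the sole report of the step trajectory. The SAP says neither. It describes change separately within each arm and states no test, interval or arm comparison for A_1.

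**Conclusion.** The point holds as one about interpretation and reporting. Under the retained model each free A_1 element is a visit's mean change divided by the arm's net change. It is unidentified at zero net change and, with at most eight patients per arm, unstable near zero: estimates can fall far outside 0 to 1, change sign, and carry Wald intervals that cover well below 95%. The SAP's reading as a share of total change can be relied on only where g_1 is large relative to its standard error, which is about 400 to 800 steps under the assumed SDs.

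The percentages above rest on assumed SDs, independent weekly errors and complete data. Fewer patients with pedometer data would worsen them. If the observed net change in an arm was several times its standard error, the coefficients there are usable. Whether the problem arose in this trial cannot be settled from the documents. The step model's fitted means, g_1 and the primary PSFS analysis are not in question.

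**What to change.** Fit the step data, or re-express the existing fit, as a linear mixed model with arm, categorical visit, arm-by-visit and a random intercept. Report for each arm the mean change from the pre-treatment week at every later visit, and the arm difference in that change, each with a 95% interval.

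Show A_1 as proportions only for an arm in which the interval for g_1 clearly excludes zero, and then with Fieller or profile-likelihood intervals, not Wald intervals. State in the SAP that A_1 is otherwise not interpreted.

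The cost is one model statement and a few lines of text, plus re-presenting a completed secondary analysis. With the same covariance structure, the data, the number of mean parameters, the fitted means and the likelihood do not change. Only the ratio display is given up.
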